9.2 Treatment interruption and treatment discontinuation

If the study drug is being held due to toxicity, scheduled visits and all assessments should continue to be performed, with the exception of the dosing of the held study drug. If treatment with the study drug is withheld for ≥ 28 days, then the study drug must be permanently discontinued. Patients who permanently discontinue the study drug should have a follow up at approximately 30 days after discontinuation of all study treatment or resolution of the adverse event to \leq grade 1, whichever occurs first, that includes all study assessments appropriate to monitor the event.

10.0 EVALUATION DURING TREATMENT/INTERVENTION

10.1 General Requirements

Table 6 describes the required procedures. All procedures may increase in frequency if clinically indicated or oriented following a toxicity/adverse event.

A complete history, vital signs (including blood pressure, pulse, respiratory rate, temperature, weight and height), physical and neurological examination (to include documentation of the patients Karnofsky performance status (Appendix 6) and NANO score as well as a serum pregnancy test for women of childbearing potential will be performed on day 1 (+/- 4 days) of each cycle.

Neuro-imaging (including contrast-enhanced MRI/CT brain and total spine) and/or CSF collection (for patients with CSF disease; through Ommaya or spinal tap; including cytology) will need to be performed on all patients on day 1 cycle 3, and each additional odd numbered cycle (+/- 4 days). Imaging will include only the side of active disease (MRI brain for patients with brain disease; MRI total spine for patients with intraspinal disease; MRI brain and total spine for patients with brain and spine disease as well as leptomeningeal disease) or sides suggested by new neurologic symptoms and signs. All MRI imaging will included MR perfusion . If MRI spectroscopy is additionally performed, we will collect the additional data.

CBC with differential, platelets, sodium, potassium, calcium, AST, ALT, alkaline phosphatase, total bilirubin, fasting plasma glucose, creatinine, will need to be performed at day 1 and day 15 of each cycle and at the end of the treatment (+/- 4 days).

Amylase and lipase need to be assessed at the end of the treatment (+/- 4 days).

Chest X-ray and 12-lead ECG need to be done every other cycle starting at day 1 of cycle 3 (+/- 4 days)

Participants need to complete the PHQ-9 and GAD7 self rating mood scale (see Appendix 6).at day 1 and day 15 of cycle 1 and 2. On each consecutive cycle only on day 1 and at the

**MEMORIAL SLOAN-KETTERING CANCER CENTER
IRB PROTOCOL**

IRB#: 14-177 A(5)

end of treatment (+/- 4 days). Questionnaires can be performed over the phone on Cycle 2 Day 15 by research staff, if the participant is not able to physically attend to clinic.

Table 6: Required Activity Calendar

Tests and procedures	Screening	On trial						
		Prior to Registration	Cycle 1		Subsequent cycles		End of treatment	30-day post drug
			Day 1	Day 15	Day 1	Day 15		
Informed consent	X							
Inclusion/exclusion criteria	X							
History, Physical and neuroexam	X	X		X		X	X	
Vital signs (blood pressure, pulse, respiration rate, temperature, height, weight) and KPS (Appendix 6)	X	X		X		X	X	
Serum pregnancy test (if applicable)	X	X		X		X		
Adverse event assessment	X			X		X	X	
Hematology group (CBC & diff)	X	X	X	X	X	X		
Chemistry group (Sodium, Potassium, Calcium, AST, ALT, Alk Phos, Total Bilirubin, Glucose, Creatinine)	X	X	X	X	X	X		
Fasting plasma glucose	X	X	X	X	X	X		
Coagulation (PT, PTT, INR)	X	X		X		X		
HbA1c	X							
8h fasting C-peptide	X							
Lipid panel	X			X*				
Amylase, lipase	X					X		
LDH	X							
Hepatitis B and C screen	X							
12-lead EKG	X			X ^s				
Chest X-ray				X ^s				
MUGA/ECHO	X							
HIV screen	X							
Bone marrow aspirate and biopsy	X							
PET brain and body	X							
PHQ-9 Patient self-rating mood scale	X		X	X	X (1)	X		
GAD7 Patient self-rating mood scale	X		X	X	X (1)	X		
NANO Score Assessment	X			X ^s		X		
Cerebrospinal fluid (CSF) Analysis including cytology	X			X(2)		X(2)		
Contrast-enhanced MRI/CT of the brain and total spine with perfusion	X			X(3)		X(3)		
Response evaluation				X (4)		X		
Computed tomography of chest, abdomen, pelvis	X							
Ophthalmologic evaluation including slit lamp exam	X							
PK BKM120 CSF			X(5)					
PK BKM120 Blood			X(6)					
Blood collection for genomic DNA			X					
Collection of archival FFPE tumor samples	X						X(7)	

- (1): PHQ-9 and GAD7 will be collected on day 15 of cycle 1 and day 1 and day 15 during cycle 2; then only on day 1 on subsequent cycles
 (2): Collection on day1 of all odd cycles starting on cycle 3; for patients with CSF disease only; response to treatment will be measured in CSF (+/- 4 days)
 (3): Imaging on day 1 of all odd cycles starting with cycle 3; MRI brain for patients with brain disease, MRI total spine for patients with intraspinal disease; MRI brain and total spine for patients with brain and spine disease as well as leptomeningeal disease (+/- 4 days)
 (4): Response will be evaluated on day 1 of all odd cycles starting with cycle 3
 (5): Patients with Ommaya reservoir: CSF collection at 1h, 2h, 4h after drug administration; no Ommaya: CSF collection through

lumbar puncture 2h after drug administration (+/- 30 min)

(6): Patients with Ommaya reservoir: Blood collect parallel to CSF collection at 1h, 2h, 4h after drug administration; no Ommaya: blood collection parallel to CSF collection through lumbar puncture 2h after drug administration (+/- 30 min)

(7): If there is a re-resection, FFPE material will be collected

* Every 3 cycles starting day 1 of cycle 3 (+/- 4 days);

§ Every other cycle starting at day 1 of cycle 3 (+/- 4 days)

% Every MRI Visit

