8.0 PRETREATMENT EVALUATION

8.1 General Requirements

All participant need to fulfill inclusion and exclusion criteria and have signed an informed consent form.

A complete history, vital signs (including blood pressure, pulse, respiratory rate, temperature, weight and height), physical, and neurological examination (to include documentation of the patients Karnofsky performance status; Appendix 6) and NANO score as well as neuro-imaging (including contrast-enhanced MRI/CT brain and total spine) and/or CSF evaluation (including cell count, total protein and glucose as well as cytology) confirming tumor progression will be performed on all patients. All patients will need a PET body and brain for staging purposes prior to study enrollment. The scans done prior to study entry documenting progression will be reviewed by the principal investigator. The baseline scan or CSF evaluation should be performed 21 days of registration. Prestudy laboratory tests need to included CBC with differential, platelets, coagulation panel (including PT, PTT, INR), sodium, potassium, calcium, AST, ALT, alkaline phosphatase, total bilirubin, fasting plasma glucose, creatinine, lipid panel, HbA1c, 8 hour fasting C-peptide, amylase, lipase, LDH, a screening hepatitis B and C serology, a screening HIV serology, serum pregnancy test for women of childbearing potential. Prestudy laboratory tests must be obtained within 21days of registration.

MEMORIAL SLOAN-KETTERING CANCER CENTER IRB PROTOCOL

IRB#: 14-177 A(5)

Documentation of tumor diagnosis. Following registration, slides from the most recent pre-registration biopsy and/or CSF cytology must be submitted for review and confirmation of diagnosis. Additionally, 20 unstained slides from the initial tissue diagnosis must be submitted for exploratory studies.

A contrast enhanced CT scan of the chest, abdomen and pelvis, ophthalmologic evaluation including slit lamp exam, 12-lead ECG, ECHO/MUGA, as well as a bone marrow aspirate must be performed for staging purposes. These staging tests must be obtained within 21 days of registration.

Patient need to complete the PHQ-9 and GAD7 self rating mood scale within 21 days of registration (see Appendix 6).

Please also see Table 6 for an overview of testing required prior to enrollment into the trial.

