11.0 TOXICITIES/SIDE EFFECTS

11.1. Anticipated toxicities

In order for an event to be expected (known correlation to the study drug) for the purposes of adverse event reporting, the event must be included in this section.

A list of adverse events of all grades suspected to be buparlisib treatment related in phase I studies, organized by CTCAE v4.0 category includes:

- Cardiovascular: Hypertension
- Gastrointestinal: Diarrhea, dyspepsia, mucosal inflammation, nausea
- General disorders: Asthenia, fatigue, pyrexia
- Investigations: Aminotransferase elevation/transaminitis, GGT elevation, hyperbilirubinemia, lymphopenia, elevated lipase
- Metabolism and nutritional disorders: Hyperglycemia, hypophosphatemia, anorexia
- Nervous system disorders: Dizziness
- Psychiatric disorders: Mood alterations including depression and anxiety
- Pulmonary: Pneumonitis
- Skin: Rash, pruritis.

The safety experience for single agent buparlisib in trial CBKM120X2101 is summarized in Table 10

Table 10: Most frequent Adverse Event (≥15%) related to study drug in study CBKM120X2101 (n=81)

Event	All grades	Grade 3/4
Fatigue/asthenia	31 (38.3%)	3 (3.7%)
Decreased appetite	24 (29.6%)	-
Diarrhea	24 (29.6%)	3 (3.7%)
Hyperglycemia	24 (29.6%)	4 (4.9%)
Nausea	24 (29.6%)	-
Rash	22 (27.2%)	4 (4.9%)
Mood altered/emotional disorder/affective disorder	17 (21%)	4 (4.9%)
Transaminases increased	16 (19.8)	9 (11.1%)
Anxiety	14 (17.3%)	1 (1.2%)
Depression	14 (17.3%)	1 (1.2%)

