Criteria for interruption and re-initiation of buparlisib treatment in case of the occurrence of AST, ALT or bilirubin increase are detailed in Section 11.2, Toxicity Management (Table 11).

Patients with clinically significant liver test abnormalities should perform liver-directed medical history, physical examination and other tests as medically indicated to assess potential relationship with study treatment and rule out other underlying causes (e.g. disease progression/obstruction, infection/hepatitis or other liver diseases, sepsis, metabolic diseases including diabetes, concomitant medications including herbals, alcohol, drug-drug interaction, cardiovascular disease/ischemia, other organ injuries, etc.). Any pre-existing liver conditions or risk factors should be reported in the respective medical history and concomitant medication CRF pages (if not done already).

All patients with ALT or AST $>$ 3.0 x ULN and total bilirubin $>$ 2.0 x ULN in the absence of cholestasis (elevation of ALP in patients without bone metastasis or if bone metastasis are present elevation of 5'-nucleotidase and ALP liver fraction) must be immediately withdrawn from buparlisib, and every attempt should be made to carry out locally the liver event follow-up assessments as described below:

- Inform the sponsor about the event immediately after its occurrence by reporting the event immediately in the clinical database if it meets the criteria for an AE or SAE.
- Evaluate if associated with the appearance or worsening of clinical symptoms of hepatitis or hypersensitivity such as fatigue, nausea, vomiting, right upper quadrant pain or tenderness, fever, rash or eosinophilia, or other organ involvement.
- Obtain fractionated bilirubin, serum Alkaline Phosphatase (ALP), creatine phosphokinase (CPK), lactate dehydrogenase (LDH), and blood count with differential to assess eosinophilia.
- Perform liver imaging (ultrasound, magnetic resonance, or computerized tomography) to evaluate liver disease including metastasis or new lesions, obstruction/compression, etc.
- Perform viral hepatitis and other serology tests:•
 - Hepatitis C (HCV) serology and viral RNA, Hepatitis B (HBV) serology and viral DNA, Hepatitis A (HAV) Immunoglobulin M (IgM) and HAV total
 - Hepatitis E (HEV) serology: IgM and IgG, viral RNA
 - Herpes Simplex Virus (HSV), Cytomegalovirus (CMV), Epstein-Barr viral (EBV) serology

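### Hypophosphatemia is named as a suspected drug effect, but phosphate is in no required test list; lipase is tested only at screening and end of treatment

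*Combined protocol and SAP*

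**What the plan says.** Section 11.1 introduces its list as "A list of adverse events of all grades suspected to be buparlisib treatment related in phase I studies". Two entries matter here: "Metabolism and nutritional disorders: Hyperglycemia, hypophosphatemia, anorexia" and, under investigations, "Aminotransferase elevation/transaminitis, GGT elevation, hyperbilirubinemia, lymphopenia, elevated lipase".

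The required tests are set in three places.

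- **Screening (Section 8.1).** After blood count, coagulation, electrolytes and liver enzymes, the list continues "total bilirubin, fasting plasma glucose, creatinine, lipid panel, HbA1c, 8 hour fasting C-peptide, amylase, lipase, LDH". Lipase is in; phosphate is not.
- **On treatment (Section 10.1 and Table 6).** Day 1 and day 15 of each 28-day cycle, and end of treatment, carry the blood count and "Chemistry group (Sodium, Potassium, Calcium, AST, ALT, Alk Phos, Total Bilirubin, Glucose, Creatinine". Neither phosphate nor lipase is in this group.
- **Lipase after screening (Section 10.1).** "Amylase and lipase need to be assessed at the end of the treatment (+/- 4 days"). The Table 6 row for amylase and lipase agrees: marks at screening and end of treatment only.

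Section 10.1 also contains a general permission: "All procedures may increase in frequency if clinically indicated or oriented following a toxicity/adverse event".

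**The concern.** A laboratory abnormality without symptoms can be found only by measuring it. The protocol names two such abnormalities as suspected effects of the drug, then schedules no phosphate test at all and no lipase test while dosing continues. Two things depend on those values.

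1. **The safety summary.** Frequency and severity of adverse events is a secondary objective (Section 2.2), reported by incidence and severity (Section 14.0). Values that are never drawn cannot be counted.
2. **The dose rule.** Section 9.1 applies Table 11 whatever the suspected cause, with a limited exception. The Table 11 row for other non-hematological events requires the dose to be omitted at grade 3, then resumed one level lower, and the drug to be stopped at grade 4. No scheduled on-treatment result can set this rule off for phosphate or lipase.

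There is a further effect for phosphate. Section 9.1 lets a laboratory toxicity count as resolved when it returns to within one grade of a pre-existing baseline abnormality. Without a baseline phosphate, that provision cannot be used.

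**Working it through.** The plan gives no figure to reproduce, so the main check is a comparison of lists.

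**Step 1. Laboratory events named in Section 11.1 against scheduled on-treatment tests**

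| Named event | Scheduled test on treatment |
|---|---|
| Aminotransferase elevation | Yes, day 1 and day 15 |
| Hyperbilirubinemia | Yes, day 1 and day 15 |
| Hyperglycemia | Yes, day 1 and day 15 |
| Lymphopenia | Yes, differential count on day 1 and day 15 |
| GGT elevation | Yes, through the Table 11 liver panel |
| Hypophosphatemia | None, and none at screening |
| Elevated lipase | None between screening and end of treatment |

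Five of the seven are covered; two are not.

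**Step 2. Every other list that might contain phosphate.** The Table 11 liver panel names albumin, ALT, AST, bilirubin, alkaline phosphatase and GGT. The Table 11 QTc work-up names potassium and magnesium. The hepatotoxicity work-up in Section 11.11.1.2 reads "Obtain fractionated bilirubin, serum Alkaline Phosphatase (ALP), creatine phosphokinase (CPK), lactate dehydrogenase (LDH), and blood count with differential to assess eosinophilia", followed by imaging and viral serology, and Table 13 is similar. Alkaline phosphatase and creatine phosphokinase are enzymes, not serum phosphate. Phosphate is in none of these lists.

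**Step 3. Count of draws.** With 28-day cycles, 24 weeks is 6 cycles, and 6 × 2 = 12 scheduled chemistry draws. Required phosphate values: 0. Required lipase values between screening and end of treatment: 0.

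**Step 4. A rough bound on size.** Table 10 lists drug-related events reported in at least 15% of 81 patients in the single-agent phase I study. Neither event is in it, so each was recorded as drug-related in fewer than 15%. Applied to this trial, 0.15 × 21 = 3.15, or at most about 3 patients for each event, all grades. This is one study, and its laboratory schedule is not given, so the bound concerns recorded events.

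**Step 5. Lipase, illustration only.** Assume a silent rise lasting L days, with onset uniform over T days on drug, and ignore visit windows. The chance that a scheduled draw catches it is:

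- end of treatment only: min(1, L/T)
- day 1 of each cycle plus end of treatment: min(1, L/28)

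| Time on drug | L = 7 | L = 14 | L = 28 |
|---|---|---|---|
| 8 weeks (T = 56), end of treatment only | 12.5% | 25% | 50% |
| 24 weeks (T = 168), end of treatment only | 4.2% | 8.3% | 16.7% |
| Either, with day 1 draws added | 25% | 50% | 100% |
| Rise that persists to end of treatment, either schedule | 100% | 100% | 100% |

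In the last row L is irrelevant because the rise is still present at the final draw. The gain in the transient case is T/28, a factor of 2 or 6, and follows directly from the assumed durations. The documents give neither the duration nor the onset pattern of lipase rises.

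**The case against.** The best reply is that the gap is small and partly covered.

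- **Discretion and adverse event assessment.** Symptomatic events will be found at visits, and Section 10.1 allows more frequent testing when clinically indicated. This stands for symptomatic events, and it permits an unscheduled lipase. It does not help with silent ones: they give no clinical indication, and the clause adds no test to any list.
- **Lipase persistence.** Dosing is continuous, so a rise that lasts as long as the drug is given would be recorded at end of treatment. This stands. A reader might infer that lipase toxicity goes unmonitored; the documents do not support that. Only silent rises that resolve before the final draw are lost from the count, though even a persistent rise would be seen too late to change dosing.
- **Rarity.** Absence from Table 10 points to few events. This stands and limits the size.
- **Harm from more testing.** Section 9.1 never permits re-escalation, so a symptomless grade 3 value would cost the patient a dose level for good, and grade 4 would end treatment. Section 9.1's exception covers only toxicity judged unrelated, which is hard to argue for events already listed as suspected drug effects. This is a real cost, but it is what the protocol's own rule prescribes for such a value.

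A reader might also infer that liver monitoring is deficient because Table 6 omits GGT and albumin. It is not: Table 11 already requires both, every other week in cycles 1 and 2 and monthly afterwards.

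**Conclusion.** The point holds and is minor. The firm part is phosphate: a named suspected drug effect with no baseline and no scheduled on-treatment test, which needs no assumption to establish. Silent hypophosphatemia would be left out of the toxicity summary and out of reach of the grade 3/4 rule. The lipase part is secondary, because screening and end-of-treatment values exist.

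The size of the under-count cannot be computed, since the documents give no rate, grade distribution or duration for either event. About 3 recorded events of each kind in 21 patients is a reasonable upper guide if the phase I frequency carries over. The lipase catch rates apply only to transient silent rises and should not be read as an estimate of missed harm.

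A reader might infer that the efficacy result is compromised. It is not: the 24-week progression-free rate and its interval are calculated without these tests. The safety objective is exploratory and descriptive, with no threshold that a missed event could cross.

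**What to change.** 1. Add phosphate to the chemistry group in Sections 8.1 and 10.1 and in Table 6, at screening, day 1, day 15 and end of treatment.
2. Add lipase to the day 1 chemistry draw of each cycle and keep the end-of-treatment test. This catches more of the silent rises that resolve early and makes a rise visible while dosing can still be changed.

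No change to amylase, GGT or albumin is needed for this point.

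**Cost.** Both tests use blood already drawn, so there is no new visit or needle. Section 17.0 bills the assay charge to the patient or insurer. More low-grade laboratory events will need recording. Some symptomless grade 3 or 4 values will lead to holds, irreversible dose reductions or discontinuation under Table 11 and Section 9.1, and the sponsor should accept that knowingly when adding the tests.

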10.2 Pharmacokinetic analysis and evaluation of study drug penetration into the CSF space

In phase I clinical trials with buparlisib, preliminary PK data showed that buparlisib accumulated ~3 fold in achieving steady state, consistent with an effective half-life of ~ 40 hours. Steady state can be reached after approximately 7-10 days of daily dosing in most participants.

On day 15 of cycle 1, patients will undergo CSF and plasma pharmacokinetic analysis. At day 15, the study drug has reached steady state. Patients with an Ommaya reservoir will undergo taps of their reservoir at 1h, 2h and 4h after drug administration. Patients without an Ommaya reservoir will undergo a single spinal tap at 2h after study drug administration. The patient will have plasma collection in parallel (patients with Ommaya reservoir: plasma collection at 1h, 2h, and 4h post drug administration; patients without Ommaya reservoir: plasma collection at 2h post drug administration. Each draw should be collected at +/- 30 min of each time point. CSF and plasma concentrations of the drug will be measured by liquid chromatography with tandem mass spectrometry to derive a CSF/plasma concentration. Samples will be stored in the [name] laboratory and analyzed at the end of the study.

10.3 End of treatment visit, including premature withdrawal and study safety follow up

All patients who discontinue study treatment, including those who refuse to return for a final visit, will be contacted for safety evaluations (i.e., assessment of AEs and/or SAEs, concomitant medications) 30 days after the last dose of study treatment. Patients whose treatment is interrupted or permanently discontinued due to an adverse event, including abnormal laboratory value, must be followed at least once a week for 4 weeks and subsequently at 4-weeks intervals until resolution or stabilization of the event, whichever comes first.

If patients refuse to return for safety evaluation visits or are unable to do so, every effort should be made to contact them by telephone to determine their status. Attempts to contact the patient should be documented in the source documents (e.g., dates of telephone calls, registered letters, etc.).

10.4 Patient self-rating mood questionnaires

The Patient Health Questionnaire-9 (PHQ-9) and Generalized Anxiety Disorder-7 (GAD-7) will be collected to screen patients for the study and to aid in the identification and severity assessment of potential mood alterations. The PHQ-9 and GAD-7 are validated (Kroenke 2001, Spitzer 2006, Spitzer 1999), patient self-administered questionnaires developed for use in clinical practices.

The PHQ-9 consists of 9 questions that assess anhedonia, depressed mood, sleep, energy, appetite, guilt and worthlessness, concentration, feeling slowed down or restlessness, and suicidal thoughts. For each of these questions, patients are asked to rate how much over the past 2 weeks they have been bothered by the symptom. Scoring of the PHQ-9 is based on a Likert-type scale from 0 to 3 (0

MEMORIAL SLOAN-KETTERING CANCER CENTER
IRB PROTOCOL

IRB#: 14-177 A(5)

indicates not at all; 1, several days; 2, more than half the days; 3, nearly every day). The sum of all nine questions is used to determine a total PHQ-9 score ranging from 0 to 27.

The GAD-7 is a one-dimensional questionnaire consisting of 7 questions. Similarly to the PHQ-9, in the GAD-7, patients are asked to indicate how often, over the past 2 weeks, they have been bothered by each of the seven core symptoms of generalized anxiety disorder as referenced in the DSM IV. Response options are “not at all” “several days” “more than half the days” and “nearly every day” scored as 0, 1, 2, and 3, respectively. The sum of all seven questions calculates the total GAD-7 score. Therefore, GAD-7 scores range from 0 to 21. The patient must complete two different mood questionnaires, (PHQ-9 and GAD-7) at Screening, at collection on day-1 or within the screening, then on day 15 of cycle 1 and day 1 and 15 of cycle 2 and on day 1 of subsequent cycles, as well as at end of treatment. Additional assessments may be done according to the clinical judgment of the investigator. All questionnaires should be administered in the patient’s local language at the beginning of the study visit prior to any interaction with the study investigator including any tests, treatments or receipt of results from any tests to avoid biasing the patient’s perspective. This is to avoid potentially biasing patients or their responses to study questionnaires.

Patients should be given sufficient space and time to complete all study questionnaires and all administered questionnaires should be reviewed for completeness. If missing responses are noted, patients should be encouraged to complete any missing responses. Attempts should be made to collect responses to all questionnaires for all patients, including from those who discontinue prior to the study evaluation completion visit, however, if patients refuse to complete questionnaires, this should be documented in study source records.

Completed questionnaires, including both responses to the questions and any unsolicited comments written by the patient, must be reviewed and assessed by the investigator before the clinical examination for responses which may indicate potential AEs or SAEs. This review should be documented in study source records.

If an AE or SAE is confirmed then the physician should record the event as instructed in section “safety monitoring and reporting” of this guidance document. The severity classification table described in Table 7 for the PHQ-9 and GAD-7 will be used in this study to increase the sensitivity of identifying potential anxiety and/or depression disorders. During the study, questionnaire scores and corresponding severity classification can be used to aid the investigator in identifying new or worsening of events. Importantly, grading must be based on the clinical interpretation of severity according to the NCI-CTCAE (v 4.03).

Table 7 Classification of severity based on mood questionnaire scores

PHQ-9 (depression)		GAD-7 (anxiety)	
Score	Severity	Score	Severity
0-4	None	0-4	None
5-9	Mild	5-9	Mild
10-19	Moderate	10-14	Moderate
20-27	Severe	≥ 15	Severe

At Screening, a patient may be judged by the investigator or a psychiatrist to be ineligible based on medical mental health history as listed in the exclusion criteria. Alternatively, patients who score ≥ 12 on the PHQ-9 or ≥ 15 on the GAD-7 mood

MEMORIAL SLOAN-KETTERING CANCER CENTER IRB PROTOCOL

IRB#: 14-177 A(5)

scale, respectively, or select a positive response of '1, 2, or 3' to question number 9 regarding suicidal thoughts or ideation will be excluded from the study.

During the treatment phase, patients who indicate a positive response by selecting '1, 2, or 3' to question number 9 in the PHQ-9 must omit treatment with study drug buparlisib and must be referred for psychiatric consultation for optimal management regardless of the total questionnaire score or CTCAE grading to confirm if study drug should be interrupted or permanently discontinued. In this specific case, the psychiatric advice can overrule the patient PHQ-9 self-assessment.

Investigators must not encourage the patients to change responses reported in questionnaires. Guidelines on how to instruct the patient to complete the questionnaires as well as how to determine the scores will be provided with each instrument. Guidance on scoring questionnaires is also provided in Appendix 5. Dosing modification guidelines for buparlisib are provided in Table 11. For additional information on AE reporting, please refer to Section Safety monitoring and reporting.

